1.0 Background and Scientific Rationale

1.1 Background Information

Approximately 50 million people in the United States suffer from some form of arthritis pain, and Osteoarthritis is the most common form of the disease. The prevalence of osteoarthritis is greater among women than men, increases with age, and affects all race/ethnicity groups.

Osteoarthritis affects articular cartilage, the smooth fibrous connective tissue essential for smooth movement and cushioning of the joint. As the disease progresses, the cartilage becomes thinner and may completely wear away. Inflammation of the synovial membrane, the lining that surrounds the knee joint and contains the synovial fluid, is often a result of these changes. Osteoarthritis can form in any joint but is more common in weight bearing joints such as the knee and hip, and results in joint space narrowing, severe pain and loss of mobility.

Ultrasound therapy for the treatment of Osteoarthritis may be used as conservative care (see reference: cochrane review).

1.2 Investigational Product Description

Low intensity therapeutic ultrasound (LITUS) will be delivered in this study using ZetrOZ's Ultrasonic Diathermy Device called sam[®]. The device package consists of a Power Controller, 2 Applicators (ultrasound generators), Ultrasound Coupling Bandages 1% Diclofenac, Ultrasound Gel, Y-Adapter, Charger and User Manual.

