1.4 Potential Risks to Subjects

The risks of using ultrasound devices to administer physical therapy are well established and include: burn, itching and/or pain. These risks decrease when using lower intensity ultrasound, as in this study. The Ultrasound Diathermy Device uses existing technology to deliver ultrasound therapy in a portable and convenient fashion. The subjects will be given the chance to ask any questions regarding the trial procedures, requirements, and purposes. Once the subjects are fully informed of the possible risks and benefits of participation in the study and all of their questions have been satisfactorily answered, they will be required to sign the informed consent form in order to participate in the study. All subjects must give consent themselves and no legally authorized representatives will be accepted on their behalf.

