2.0 Study Objectives and Design

2.1 Objectives

Evaluate the usability of the device for proper design.

[figure not shown]
Evaluate the ability of LITUS to reduce pain, stiffness as measured by NRS scale and the Western Ontario and McMaster Universities Arthritis Index (WOMAC)

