2.2.2 Study Design Schematic

3.0 Study Population

3.1 General Characteristics of the Proposed Subject Population(s)

This study will enroll subjects with physician confirmed knee Osteoarthritis pain. The long duration wearable therapeutic ultrasound treatment has multiple benefits likely to aid the patients enrolled in this study with knee Osteoarthritis pain. Acoustic waves mechanically stimulate tissue, triggering biological effects including the down regulation of inflammatory cytokines, increased transport kinetics, protein synthesis, and extracellular matrix deposition. It is therefore hypothesized that the wearable device has the potential to provide sustained OA symptom management.

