3.3 Inclusion Criteria

Subjects to be enrolled in the trial will:

- Have physician-diagnosed mild to moderate knee OA (OARSI atlas grades 1-2)
- Fulfill the American College of Rheumatology clinical and radiological diagnostic criteria for knee OA
- Are between 35-80 years of age
- Report a frequent pain score between 3-7 (range: 0-10) during the week preceding enrollment
- Report that knee pain negatively affects quality of life
- Are willing not to use any cream, gel, or topical solution during the administration of treatment other than the approved ultrasound gel provided to the subject at the initiation of the study
- Are deemed appropriate by their physician or by the study site physician to participate.
- Be willing and able to self-administer treatment daily within their place of residence or during normal daily activity, excluding bathing, showering, or other water activities which may result in submersion of the study device.
- Not use or initiate opioid and/or non-opioid analgesic medications.
- Be willing to discontinue any other interventional treatment modalities on the knee during the study period (e.g., transcutaneous electrical nerve stimulation, electronic muscle stimulation, traditional ultrasound).

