4.3 Study Treatment

4.3.1 Treatment Groups

Subjects will participate in one treatment arm. All devices are manufactured by ZetrOZ Systems (Trumbull, CT) and are all identical. The 3 MHz device was FDA cleared in November 2013, and is marketed in the United States under the brand name sam[®]. All study subjects will apply 2 applicators affixed to the coupling bandages to their knee on the medial and lateral sides as shown in the figure below. The applicators are connected via a Y-adapter to a single power controller. The subjects will set the power controller to a 4-hour treatment duration for each daily treatment.

Sample Applicator Placement

This device delivers continuous ultrasound with a maximum acoustic power output of 1.3 W/cm² ±20% when 2 applicators are used. The frequency is 3 MHz ± 20%. The maximum treatment duration permitted is 4 hours per day.

Treatment protocol: subjects will self-administer the LITUS therapy for 4 hours per day at least 5 days (and up to 7 days) for the 1-week study.

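### Section 1.2 lists the coupling bandages as 1% diclofenac, but no other section accounts for a drug; the composition must be settled before enrolment

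*Combined protocol and SAP*

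**What the plan says.** Section 1.2 (Investigational Product Description) itemises the device package and includes "Ultrasound Coupling Bandages 1% Diclofenac". Section 4.3.1 (Treatment Groups) makes the bandages part of treatment for everyone: "All study subjects will apply 2 applicators affixed to the coupling bandages to their knee on the medial and lateral sides". The dosing rule in the same section is that "subjects will self-administer the LITUS therapy for 4 hours per day at least 5 days (and up to 7 days) for the 1-week study".

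The sections that say what is being tested do not mention a drug. The efficacy objective in 2.1 is to "Evaluate the ability of LITUS to reduce pain, stiffness as measured by NRS scale" and WOMAC. The hypothesis in 1.3 credits improvement to the LITUS device. The rationale in 3.1 is acoustic: "Acoustic waves mechanically stimulate tissue, triggering biological effects including the down regulation of inflammatory cytokines", among other effects.

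On risk, section 1.4 says: "The risks of using ultrasound devices to administer physical therapy are well established and include: burn, itching and/or pain". On eligibility, two inclusion criteria in 3.3 touch on drugs. One concerns topicals: "Are willing not to use any cream, gel, or topical solution during the administration of treatment other than the approved ultrasound gel". The other concerns analgesics: "Not use or initiate opioid and/or non-opioid analgesic medications". The exclusions in 3.4 include current steroid use, but none names an NSAID.

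**The concern.** A named drug at a named strength, in the section that defines the investigational product, is hard to treat as boilerplate. If the entry is right, two things follow.

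- **Safety.** Every subject would have a topical NSAID against the skin on each treatment day. The risk section would not describe that drug, and no criterion would prompt a screener to ask about NSAID or diclofenac allergy.
- **Conclusion.** The intervention would be ultrasound plus an analgesic. Section 5 compares NRS before and after each treatment and WOMAC on days 1 and 7, using t-tests and repeated-measures ANOVA. With one arm and both components given to everyone, none of these analyses can separate them. Reporting the change as what LITUS achieved would misname what was given.

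If the entry is wrong, the product description is wrong. Either way the text needs correcting. The usability objective is not affected.

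**Working it through.** The plan gives no figure on this point to reproduce, so the check is a comparison of sections plus three counts.

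**1. Can the documents settle the composition?** References to bandages or patches: one in 1.2, one in 4.3.1, one in 4.3.4 (the count of remaining bandages) and three in the 4.6 schedule (device distributed with patches, patches distributed, unused patches collected). Total: 1 + 1 + 1 + 3 = 6. One of the six names diclofenac and none says drug-free. The question therefore rests on a single list entry that nothing confirms or contradicts. If a comma has been lost and diclofenac is a separate item, the package still contains it.

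**2. Is the drug accounted for elsewhere?**

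| Section | What it names | Diclofenac mentioned? |
|---|---|---|
| 1.3 Hypotheses | LITUS device | No |
| 1.4 Risks | Burn, itching, pain from ultrasound | No |
| 2.1 Objectives | LITUS | No |
| 3.1 Rationale | Wearable therapeutic ultrasound, acoustic waves | No |
| 4.3.1 Treatment | Applicators on coupling bandages | No |

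**3. Is there a drug-specific screen?** Criteria: 10 in 3.3 + 16 in 3.4 = 26. Criteria naming NSAID or diclofenac allergy or contraindication: 0 of 26. Related protection does exist:

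- Section 3.4 excludes pregnancy, hereditary bleeding tendency, and open sores or wounds in the treatment area.
- Section 3.3 bars opioid and non-opioid analgesics, which covers concurrent NSAID use.
- Two general criteria could catch a contraindication: physician appropriateness (3.3) and investigator judgment (3.4).
- Section 4.6 schedules medical history, treatment history and physical examination at screening.

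The remaining gap is NSAID or diclofenac allergy, and any contraindication that those items miss.

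**4. How long is treatment?** From 4.3.1: 4 hours × 5 days = 20 hours, and 4 hours × 7 days = 28 hours per subject. This is device treatment time. No section says how long a bandage stays on or how much drug it would deliver, so it is neither a drug dose nor a measure of bias or risk.

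**The case against.** The strongest reply is that the harm is conditional. The documents do not establish that the bandages contain a drug, and a mistaken entry in 1.2 would need only one wording correction. That stands. High confidence attaches to the inconsistency, not to the safety or attribution harm.

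A second reply is that the single-cohort case series in 2.2.1 has no control, so change could not be credited causally to LITUS whatever the bandage contains. That also stands. A reader might infer that diclofenac is what prevents attribution to LITUS, but the design already does. The added problem is an intervention that leaves out an analgesic by name.

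A third reply concerns 3.3. A reader might infer that its rules, taken literally, bar the study's own bandage. The documents do not support so firm a reading. The topical rule covers creams, gels and solutions, and a bandage is none of these by name. The analgesic rule is the more direct conflict, since it is not limited by formulation, but it can be read as governing the subject's own medication. Section 4.5, by addressing non-study drugs, is compatible with that reading. What remains is an ambiguity: the ultrasound gel is exempted by name and the bandage is not.

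Finally, general safeguards and several specific exclusions already reduce the safety gap. They narrow it without closing it, because 1.4 and 3.4 give the screener no prompt to ask about NSAID allergy.

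**Conclusion.** The point holds as an inconsistency that must be resolved before enrolment. Section 1.2 names a drug that the hypothesis, risks, objective, rationale, treatment description and all 26 eligibility criteria do not account for, and no section resolves the conflict. Either 1.2 is wrong, or 1.3, 1.4, 2.1, 3.1, 3.4 and 4.3.1 are incomplete and 3.3 needs clarifying.

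The safety and attribution consequences rest on one assumption: that the bandages are medicated as listed. The documents give no figure for the drug's effect or risk, so none is stated here.

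Two further inferences are tempting and unsupported. One is that subjects were not told about a drug: the consent form and user manual were not available for review, so this is not judged. The other is that an added allergy exclusion would endanger recruitment: the documents give no basis for estimating how many more subjects would fail screening.

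**What to change.** Confirm the bandage composition before enrolment. This is the step that cannot be skipped.

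If the bandages are medicated:

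- (a) Name the intervention as the sam device with 1% diclofenac coupling bandages in 1.3, 2.1, 3.1, 4.3.1 and the final report, so that NRS and WOMAC changes are not reported as an effect of LITUS alone.
- (b) Add diclofenac risks to 1.4.
- (c) Add NSAID or diclofenac allergy or contraindication to the exclusions in 3.4.
- (d) As a clarification, state in 3.3 that the study-supplied bandage is exempt from the analgesic and topical rules.

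If the bandages are drug-free, correct 1.2 only.

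The cost in the drug-free case is one wording correction. In the medicated case it is protocol wording, one screening question, a narrower efficacy claim and possibly a few more screen failures, a number the documents do not allow to be estimated.

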1.3 Hypotheses

It is hypothesized that users of the LITUS device (sam®) device will be able to successfully apply and remove the device daily to the knee. It is hypothesized that treatment with the LITUS device (sam®) will yield improvements in pain and stiffness in subjects with knee Osteoarthritis.

1.4 Potential Risks to Subjects

The risks of using ultrasound devices to administer physical therapy are well established and include: burn, itching and/or pain. These risks decrease when using lower intensity ultrasound, as in this study. The Ultrasound Diathermy Device uses existing technology to deliver ultrasound therapy in a portable and convenient fashion. The subjects will be given the chance to ask any questions regarding the trial procedures, requirements, and purposes. Once the subjects are fully informed of the possible risks and benefits of participation in the study and all of their questions have been satisfactorily answered, they will be required to sign the informed consent form in order to participate in the study. All subjects must give consent themselves and no legally authorized representatives will be accepted on their behalf.

2.0 Study Objectives and Design

2.1 Objectives

Evaluate the usability of the device for proper design.

[figure not shown]
Evaluate the ability of LITUS to reduce pain, stiffness as measured by NRS scale and the Western Ontario and McMaster Universities Arthritis Index (WOMAC)

2.2 Study Design

2.2.1 General Study Design

This study is designed as a single cohort case series. After screening and enrollment, subjects will self-administer LITUS daily for 7 consecutive days.

2.2.2 Study Design Schematic

3.0 Study Population

3.1 General Characteristics of the Proposed Subject Population(s)

This study will enroll subjects with physician confirmed knee Osteoarthritis pain. The long duration wearable therapeutic ultrasound treatment has multiple benefits likely to aid the patients enrolled in this study with knee Osteoarthritis pain. Acoustic waves mechanically stimulate tissue, triggering biological effects including the down regulation of inflammatory cytokines, increased transport kinetics, protein synthesis, and extracellular matrix deposition. It is therefore hypothesized that the wearable device has the potential to provide sustained OA symptom management.

3.2 Anticipated Number of Research Subjects

Enrollment will be monitored at the assumed rates of Screen Failures and Discontinuation may be found to differ in this study from historical controls. The objective is to screen and enroll towards a target of 30 completed subjects.

Subjects to be Screened		50
Assumed Screen Fail Rate	30%	
Subjects to be Enrolled (sign ICF)		35
Assumed Discontinuation Rate	10%	
Total Number Completers (complete 24-wk treatment phase)		30

3.3 Inclusion Criteria

Subjects to be enrolled in the trial will:

- Have physician-diagnosed mild to moderate knee OA (OARSI atlas grades 1-2)
- Fulfill the American College of Rheumatology clinical and radiological diagnostic criteria for knee OA
- Are between 35-80 years of age
- Report a frequent pain score between 3-7 (range: 0-10) during the week preceding enrollment
- Report that knee pain negatively affects quality of life
- Are willing not to use any cream, gel, or topical solution during the administration of treatment other than the approved ultrasound gel provided to the subject at the initiation of the study
- Are deemed appropriate by their physician or by the study site physician to participate.
- Be willing and able to self-administer treatment daily within their place of residence or during normal daily activity, excluding bathing, showering, or other water activities which may result in submersion of the study device.
- Not use or initiate opioid and/or non-opioid analgesic medications.
- Be willing to discontinue any other interventional treatment modalities on the knee during the study period (e.g., transcutaneous electrical nerve stimulation, electronic muscle stimulation, traditional ultrasound).

3.4 Exclusion Criteria

A potential subject will be excluded from participation in this study if he or she:

- Cannot successfully demonstrate the ability to put on and take off the device.
- Displays any condition which, in the judgment of the investigator, would make participation in the study unacceptable including, but not limited to, the subject's ability to understand and follow instructions.
- Participated in a clinical trial for an investigational drug and/or agent within 30 days prior to screening.
- Is pregnant.
- Is a prisoner.
- Is non-ambulatory (unable to walk).
- Has a pacemaker.
- Has a malignancy in the treatment area.
- Has an active infection, open sores, or wounds in the treatment area.
- Has impaired sensation in the treatment area, such as caused by chemotherapy or anesthesia.
- Has a known neuropathy (disease of the brain or spinal nerves).

- Has a hereditary disposition (tendency) for excessive bleeding (hemorrhage).
- Have knee replacement, other surgical intervention, or hyaluronidase injection in the affected knee in the past 6 months
- Are currently taking steroids
- Have any contraindication to radiograph
- Have a secondary cause of arthritis (metabolic or inflammatory)

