4.5 Use of Non-Study Drugs and Procedures

Not Applicable. Not Allowed.

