5.0 Data Management and Analysis

5.1 Outcome Measures and Data Analysis Plan

5.2 Change in NRS pain score from baseline will be analyzed for pre and post-treatment each treatment day throughout the study, and WOMAC (pain, stiffness, and functional change) will be evaluated on day 1 and day 7. Data will be analyzed using t-tests and repeated measure ANOVAs.

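### The 6-month knee-injection exclusion in 3.4 names hyaluronidase, so read literally it misses hyaluronic acid, and the steroid criterion leaves it unclear whether a recent knee injection is covered

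*Combined protocol and SAP*

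**What the plan says.** Two criteria in section 3.4 bear on earlier treatment of the knee. One sets a 6-month look-back: "Have knee replacement, other surgical intervention, or hyaluronidase injection in the affected knee in the past 6 months". The other concerns steroids: "Are currently taking steroids". It names no route, joint or period.

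Other restrictions apply to current or on-study treatment. Section 3.3 requires subjects to "Be willing to discontinue any other interventional treatment modalities on the knee during the study period", with stimulation devices and conventional ultrasound as its examples. It also has an analgesic rule, "Not use or initiate opioid and/or non-opioid analgesic medications". Section 4.5, on non-study drugs and procedures, reads in full "Not Applicable. Not Allowed".

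Two clauses leave room for judgment. Section 3.3 asks that a physician consider the subject appropriate. Section 3.4 excludes anyone who "Displays any condition which, in the judgment of the investigator, would make participation in the study unacceptable".

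The Schedule of Assessments (4.6) records treatment history at V1, but no section says how it is used.

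On design, section 2.2.1 states: "This study is designed as a single cohort case series". Section 5 analyses NRS change from baseline, and "WOMAC (pain, stiffness, and functional change) will be evaluated on day 1 and day 7", by t-tests and repeated-measures ANOVA. It plans no covariate or subgroup for prior treatment.

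**The concern.** A 6-month look-back tied to the affected knee shows that the sponsor wanted recent procedures and injections kept out. The wording may not achieve this. A subject who received hyaluronic acid shortly before screening does not meet the criterion as written. A subject who had a single steroid injection into the study knee some weeks earlier could truthfully say that he or she is not taking steroids.

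With no control arm, whatever an earlier injection does to pain during the study week enters the mean change alongside any device effect. The planned analyses do not identify the subjects concerned.

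**Working it through.** **1. Does another criterion close the gap?**

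- Knee modalities (3.3): applies during the study period, so it cannot reach an injection already given.
- Analgesics (3.3) and non-study drugs and procedures (4.5): neither states a pre-enrolment period.
- Physician and investigator judgment (3.3, 3.4): permits exclusion but does not require it, and does not mention injections.
- Treatment history (4.6): collected, but not linked to eligibility or analysis.

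None expressly excludes either kind of subject.

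**2. The plan's own numbers.** Section 3.2 gives 50 screened, 35 enrolled and 30 completers, with 30% screen failure and 10% discontinuation. 50 × (1 − 0.30) = 35, and 35 × (1 − 0.10) = 31.5, which supports the target of 30. The documents give no SD, effect size or power, and nothing on how many subjects have had injections.

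**3. Size of a possible shift (assumptions only).** Let f = k/30 be the share of completers with a recent injection, and d the change in NRS that the injection causes *within the study week* (positive if pain falls further, negative if the effect wears off). An effect constant from baseline to day 7 has d = 0 and cancels.

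Shift in mean change = f × d

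| Assumed within-week change | k = 3 (f = 10%) | k = 6 (f = 20%) |
|---|---|---|
| Fast: 2 points in the week | 2 × 3/30 = 0.20 | 2 × 6/30 = 0.40 |
| Slow: a 2-point effect fading evenly over 12 weeks, 2/12 = 0.17 per week | 0.17 × 3/30 = 0.02 | 0.17 × 6/30 = 0.03 |

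The slow row is a waning effect, so its shift goes against the device. The fast row can take either sign.

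**4. Effect on a paired t-test.** Assume 30 completers, two-sided 5%, an SD of change of 2 and no device effect. The SD including the mixture is √(SD² + f(1 − f)d²), and the non-centrality is f × d / that SD × √30.

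- f = 10%, d = 2: SD = √(4 + 0.36) = 2.09; chance of a significant result 8.0% (10.1% with SD 1.5, 7.0% with SD 2.5).
- f = 20%, d = 2: SD = √(4 + 0.64) = 2.15; chance 16.6% (23.8% with SD 1.5, 12.7% with SD 2.5).
- A shift of 0.05 (f = 5%, d = 1): chance 5.2%. The slow-fade shifts of 0.02 to 0.03 are smaller still, so the test stays close to its nominal 5%.

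These chances are two-sided. If d is negative, the excess significant results are in the direction of worsening.

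**The case against.** The strongest reply is that this is a wording slip of little consequence. In an osteoarthritis study, an injection criterion tied to the affected knee will probably be read as hyaluronic acid, and at a single site the investigator or a sub-investigator goes through eligibility with the subject (4.1, 4.2). The checklist itself is not in the documents and may already be right. The steroid criterion is not restricted by route, so a physician could count a recent depot injection as current use. The first listed objective is usability, and without a control arm the change cannot be attributed to the device whether or not 3.4 is amended.

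Most of this stands and limits the weight of the point. It does not remove it: an eligibility rule should not depend on the reader correcting it, and the steroid ambiguity remains even if the hyaluronidase slip is silently corrected.

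A reader might infer three stronger things that the documents do not support.

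- *That an injection's effect is counted as device effect.* The outcome is change from baseline, so only movement within the 7 days enters, and a waning effect makes the device look worse.
- *That nothing limits the number of injected subjects.* The judgment clauses are partial limits. So is the required pain score of 3 to 7 in 3.3, which keeps out anyone whose pain an injection has brought below 3.
- *That the 6-month window should extend to every injection into the joint.* No section supports that window for steroids. It would be a clinical rule of the reviewer's own making.

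**Conclusion.** The point holds as a defect of wording in an operative criterion, together with an ambiguity in a second one. Read literally, 3.4 does not exclude recent hyaluronic acid injection, and it does not settle whether a recent steroid injection into the study knee counts. That hyaluronic acid was intended is an inference, because the documents never name it.

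The consequence is a possible shift in mean NRS change, of either sign, that the planned analysis cannot separate from a device effect. Its size is unknown and probably small. The 0.02 to 0.4 points shown rest on an assumed 3 to 6 injected completers of 30 and an assumed within-week change of 0.17 to 2 points. The upper end needs 2 points of movement in a single week, for which the documents offer no support. The correction is worth making because it is specific and cheap, not because a large bias has been shown.

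**What to change.** 1. In 3.4, correct the injected substance so that the criterion names what the sponsor intends, and make the Eligibility Screening Checklist match.
2. Reconcile the injection and steroid criteria by stating whether recent steroid injections of the study knee are covered. Any window is for the sponsor to set.
3. In section 5, use the V1 treatment history to identify previously injected subjects, report their number, and add a sensitivity analysis of NRS and WOMAC change without them.

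The first two need a short amendment to 3.4 and the checklist; the third needs a sentence in section 5 and no new data.

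The downside is possibly a few more screen failures than the assumed 30%, with little slack to absorb them. At 10% discontinuation, 30 completers need 30/0.90 = 33.3, so 34 enrolled against the planned 35. Two extra failures would leave 33 × 0.90 = 29.7, so one or two more subjects might have to be screened. The sensitivity analysis loses some precision: without 3 or 6 of 30 subjects, the standard error grows by √(30/27) = 1.05 or √(30/24) = 1.12 at an unchanged SD.
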